## **Method**

### **Experimental Design**

A three-group by two-assessment mixed prospective design will be used in this study. Participants will be randomly assigned to the order of each group and condition. See *Figure 1* for flowchart of the proposed study.

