### **Procedure**

The participants in the study will be recruited through advertisements in local newspapers, posted flyers on the campus of West Virginia University, and advertised on Craigslist (e.g., a website that provides services/goods). Upon arrival to the study, participants will be given a written informed consent form and information on study procedures. The researchers will discuss the process of the study and what is expected of the participant. The participants will be informed that they will receive \$40.00 for compensation at the completion of the study. After agreement to enlist in the study and completion of the ADIS-5, the participants will be randomly assigned to group (i.e., 2-week waitlist or treatment group) by previously prepared sealed opaque envelopes, complete the demographic questionnaire, conducted the DBAT, and answer the DFS. The researchers will then provide a 15-minute demonstration on how to conduct self-directed exposure therapy on the participant's mobile phone, and how to rate

SUDS. The researchers will describe that watching the exposure video three times per day is the ideal, one time per day is the suggested minimum, and viewing the exposure video five times per day is the suggested maximum.

The video will display a typical preventive visit to the dentist, including walking into the dental office, being called back for treatment by the dental assistant, sitting in the dentist chair, and seeing the dentist perform a teeth cleaning. The video will be 15-minutes in length, and be recorded by the researchers in both first- and third-person perspective. The actors in the video will be confederates and have knowledge about the purpose of the video. The actors in the video are from the School of Dentistry at West Virginia University.

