Participants in the treatment group will receive daily text messages as a reminder to conduct the exposure. Participants will be asked to follow the link and sign in each day with their mobile phones. Before each exposure video, the participants will rate expected distress on the SUDS. Then the participants will be asked to watch a video depicting dental care-related phobic material. After viewing the exposure video, participants will rate actual distress experienced on the SUDS. The participants will then be prompted to watch the video again. If the participant decides to view the video again, they will go through the same procedure of pre-rating fear and anxiety, watching the video, and post-rating fear and anxiety. Finally, the participants will be prompted to complete the procedure once more. After completing the procedure three times, the participants will no longer be prompted, however, they have the ability to complete the procedure two more times if they so desire.

The participants in the treatment group will be randomly assigned by previously prepared sealed opaque envelopes to video content (i.e., first- or third-person perspective). After 1-week of first or third video perspective, the participants will be assessed by the researcher via

telephone. Questions on the PQ and the DFS will be answered by the participants. After the assessment, participants in the first-person perspective will be informed that the video content will change to third-person perspective. Participants in the third-person condition will be informed that the video content will change to first-person perspective. At the end of the two weeks, participants will be asked to return in person for a follow-up and to receive \$40.00 compensation. The follow-up assessment will consist of the DBAT, completing the DFS, answering the PQ, and rating acceptability of using a mobile phone as a mean of self-directed exposure.

The control group will be assessed on the DFS after one week via telephone. After the two weeks the participants in the control group will be asked to return for a follow-up assessment and receive \$40.00 compensation. The assessment will consist of the same as the treatment group. At the follow-up session, participants in the control group will be offered the same treatment, for ethical reasons, as the experimental group, however, the data will not be analyzed.

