Proposed Analyses

Rates of procedure adherence (i.e., watching the video at least three times daily) will be assessed in order to examine the study's first question. The second question will be assessed by examining participants' rating of acceptability on the AARP with using a mobile phone as a method for self-directed exposure.

There will be 3 (group) x 2 (assessment) mixed measures analyses of variance (ANOVAs) which will be conducted to assess the first hypothesis regarding treatment effectiveness, with the DFS, and various DBAT measures (i.e., avoidance/escape, cardiac response, and SUDS verbal reports) as dependent variables. Sensitivity analyses will be conducted for baseline measurements. In order to examine the second hypothesis, a paired sample *t*-test assessing the relation of video perspective and scores on the PQ will be conducted.

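### The DBAT outcomes are tested by a change-score analysis; ANCOVA on the first-visit DBAT value already collected would probably be more efficient, by an amount the documents do not fix

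*SAP*

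**What the plan says.** The Protocol (Experimental Design) states: "A three-group by two-assessment mixed prospective design will be used in this study". The SAP (Proposed Analyses) carries this into the analysis: "There will be 3 (group) x 2 (assessment) mixed measures analyses of variance (ANOVAs) which will be conducted to assess the first hypothesis". The dependent variables are the DFS and "various DBAT measures (i.e., avoidance/escape, cardiac response, and SUDS verbal reports) as dependent variables". The SAP does not say which term of the ANOVA (group, assessment or their interaction) tests Hypothesis 1.

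The Protocol (Procedure) places a DBAT at the first visit, where participants are assigned "by previously prepared sealed opaque envelopes, complete the demographic questionnaire, conducted the DBAT, and answer the DFS". There is a second DBAT at two weeks in the treatment group ("The follow-up assessment will consist of the DBAT, completing the DFS, answering the PQ") and in the control group ("The assessment will consist of the same as the treatment group"). The week-1 telephone contact includes the DFS but no DBAT. Each DBAT outcome is therefore measured exactly twice in every group.

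On baseline, the SAP says only: "Sensitivity analyses will be conducted for baseline measurements". It names no model, covariate or rule for when these analyses apply.

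**The concern.** Hypothesis 1 predicts greater fear reduction with exposure than in the control group, so the group x assessment interaction is the term that addresses it. With two assessments that interaction is a comparison of mean change. A change score subtracts the whole baseline value, which amounts to a baseline regression slope fixed at 1. ANCOVA estimates the slope from data the trial already collects. In a randomised comparison with a baseline taken before assignment, both methods estimate the same treatment effect, so the choice between them is mainly one of precision.

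At stake is power on three of the four kinds of outcome named for Hypothesis 1, in a trial of 36. Chance baseline differences also matter with about 12 per group: a change score over-corrects for them whenever the true slope is below 1. Because the baseline sensitivity analyses are not defined, the choice of adjusted model is left open until the data are in hand.

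**Working it through.** **Inputs.** From the Protocol (Participants): three groups, two measurements, effect size f = .25, power .80, total N of at least 36. Assumed, because not stated: alpha .05, 12 per group, no dropout. Also assumed: a correlation r of .3 to .7 between first-visit and week-2 DBAT values, with equal SDs at the two visits (relaxed in step 5).

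**1. The plan's own figure.** For repeated-measures tests, lambda = f² x N x 2/(1 - r), with error df = N - 3.
- Assessment (time) effect, 1 df, r = .5: minimum N is 34, or 36 in three equal groups. The stated 36 is reproduced.
- Group x assessment interaction, 2 df, r = .5: lambda at N = 36 is .0625 x 36 x 2/.5 = 9.0, power .73; 80% power needs N = 42.
- The same interaction at r = .6: minimum N is 35, or 36 in equal groups (power .83 at 36).

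So 36 gives 80% power for the interaction only if r is about .58 or more.

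**2. Equivalence.** With two assessments, the interaction F equals the one-way ANOVA F on (week 2 - first visit).

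**3. Residual variances, equal SDs (in units of SD²).** Change: 2(1 - r). ANCOVA: 1 - r². Ratio: (1 + r)/2, so the cut is (1 - r)/2. Estimating the slope with 12 per group inflates the variance of the adjusted contrast by about 1 + 1/31 = 1.032.

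| r | Ratio | Cut | Ratio x 1.032 | Net cut |
|---|---|---|---|---|
| .3 | .65 | 35% | .671 | 33% |
| .5 | .75 | 25% | .774 | 23% |
| .7 | .85 | 15% | .877 | 12% |

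**4. Power at N = 36.** Take group effects (0, D, D): waitlist against two video orders with equal benefit at week 2. The sum of squares is 12 x (4/9 + 1/9 + 1/9) x D² = 8D². The protocol's f = .25 corresponds to D = 1.06 SD: at r = .5, 8 x 1.06²/1 = 8.99, against the 9.0 in step 1. Lambda is 8D² divided by the residual variance; df are 2 and 33 for change, 2 and 32 for ANCOVA.

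| r | D = 1.06: change, ANCOVA | D = 0.8: change, ANCOVA |
|---|---|---|
| .3 | .57, .77 | .35, .51 |
| .5 | .73, .85 | .48, .60 |
| .7 | .92, .96 | .71, .78 |

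The ANCOVA powers are before the slope-estimation cost. With it, the r = .5, D = 1.06 figure is about .84. Simulation with normal data (6,000 trials per setting) gave .734 and .844 at that point. Type I error across r = .3 to .88 was .047-.054 for change and .044-.049 for ANCOVA, and the mean estimated effects agreed.

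**5. Unequal SDs.** With k = week-2 SD/first-visit SD, the cut is 1 - k²(1 - r²)/(1 + k² - 2rk).
- k = 0.8: 50%, 43% and 37% at r = .3, .5 and .7.
- k = 1.2: 24%, 13% and 3%. At r = .7 the slope-estimation cost absorbs nearly all of it: .734/.760 x 1.032 = .997.

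**The case against.** **The planned test is sound.** It holds its type I error and estimates the same effect. This stands: the point is about efficiency, not an error in the plan.

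**The size of the gain is unknown.** This stands too. No DBAT correlation or SD is given. The only correlation in the documents is the DFS test-retest value of .88 (Protocol, Self-Report Measures); at that value and equal SDs the cut would be 6%. It belongs to another instrument and cannot be carried over to the DBAT. The residual variance under ANCOVA is never larger, but if the true slope were 1, estimating it would cost about 3%.

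**The first DBAT may not be a true baseline.** The Procedure lists assignment before it. Suppose knowing the group shifts the first DBAT by d in one arm relative to the other (equal SDs). If the shift does not last to week 2, change is biased by d and ANCOVA by about r x d. If it persists, it cancels in the change score and leaves ANCOVA biased by about (1 - r) x d. Neither method is safe in both cases. The remedy is the order of steps, not the choice of model.

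**Linear models may fit avoidance seconds poorly.** The DBAT has eight steps of up to 60 seconds, so the score is bounded at 480 and may have many zeros. This strains both models and is no reason to fix the slope at 1, but the figures above are normal-theory and only approximate for that outcome.

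**Hypothesis 1 would rest on two kinds of model.** The DFS has a third, week-1 assessment, and the SAP does not say which two enter its ANOVA, so it needs its own decision. This point is confined to the DBAT.

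**Baseline has been considered.** A reader might infer that the sensitivity analyses amount to a planned ANCOVA, or that adjustment will follow only from a significant baseline difference. The SAP says neither. What can be said is that the model is unspecified.

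**Conclusion.** The point holds as a matter of efficiency. For each DBAT outcome the interaction test is a change-score test, and ANCOVA uses the same data with residual variance no larger at any correlation. With r of .3 to .7, equal SDs, 12 per group and alpha .05, all assumed, the cut in residual variance is 35% to 15%, or about 33% to 12% net. At r = .5, power for the protocol-sized effect moves from about .73, below the .80 target, to .84-.85. With SD ratios of 1.2 or 0.8 the cut is 3-24% or 37-50%.

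Two stronger readings are tempting. A reader might infer that the mixed ANOVA is invalid; the simulated error rates and effect estimates show it is not. A reader might also take 15-35% as a property of this trial; it follows from assumed inputs, and the documents supply no DBAT figure to confirm it. The change is worth making because it costs almost nothing, the gain is likely though of uncertain size, and it settles an analysis choice now left open.

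**What to change.** In the SAP, Proposed Analyses:

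1. For each DBAT outcome, make the Hypothesis 1 analysis an ANCOVA of the week-2 value on group (three levels), with the first-visit value of the same outcome as covariate. Apply it unconditionally, with no baseline significance testing.
2. For cardiac response, define one summary and compute it the same way from both DBATs. The covariate is that summary from the first-visit DBAT, not the resting recordings made within a DBAT session.
3. Report the 2-df group test and the adjusted treatment-versus-waitlist differences with 95% confidence intervals.
4. Keep the 3 x 2 mixed ANOVA as the sensitivity analysis, naming the group x assessment interaction as the term of interest. Let this replace the general sentence on baseline sensitivity analyses.
5. Note that avoidance seconds are bounded and may be skewed, so the normal-theory gain is approximate there.

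In the Protocol, Procedure: state that the first DBAT and DFS are completed before the envelope is opened.

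Cost: SAP wording, the order of steps at the first visit, and one error degree of freedom per model (32 instead of 33 at N = 36). No new data are needed.

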## **Study Protocol**

The proposed study will examine the question of whether phobic individuals will use a mobile phone in self-directed exposure therapy. A second question is whether phobic participants will find the use of a mobile phone as an acceptable means of conducting self-directed exposure therapy.

Accompanying these two research questions are additional specific hypotheses. The first hypothesis is that filmed exposure stimuli, available on a mobile phone, will be associated with greater fear reduction in a self-directed exposure group relative to a control group. The second hypothesis is that greater presence will be reported with first-person perspective versus third-person perspective.

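### Hypothesis 2: the paired t-test is valid but ignores the randomised order; a period term would protect power if presence ratings shift on average between week 1 (telephone) and week 2 (in person)

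*SAP*

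**What the plan says.** The second hypothesis (Protocol, Study Protocol) is that "greater presence will be reported with first-person perspective versus third-person perspective". The SAP (Proposed Analyses) tests it in one clause: "a paired sample *t*-test assessing the relation of video perspective and scores on the PQ will be conducted". It names no period, order or sequence term.

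The data come from a crossover, described in the Protocol under Procedure:

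- **Randomised start.** Treatment participants "will be randomly assigned by previously prepared sealed opaque envelopes to video content (i.e., first- or third-person perspective"). Experimental Design also says: "Participants will be randomly assigned to the order of each group and condition".
- **Week 1 rating, by telephone.** The text reads "telephone. Questions on the PQ and the DFS will be answered by the participants".
- **Switch.** After that call, "participants in the first-person perspective will be informed that the video content will change to third-person perspective", and the other order switches the opposite way. No washout is described.
- **Week 2 rating, face to face.** At two weeks "participants will be asked to return in person for a follow-up". "The follow-up assessment will consist of the DBAT, completing the DFS, answering the PQ" and an acceptability rating. The sequence of tasks within that visit is not stated.

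The allocation ratio of the envelopes, any blocking and the number treated are not given. Participants (Protocol) gives only a total of at least 36.

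**The concern.** The two presence ratings that each person contributes differ in more than video perspective. Mode changes from telephone to in person. Setting changes, because the second visit includes a simulated dental examination. A further week of viewing has also passed. Any of these could move the average rating whichever perspective was watched.

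Randomising the order stops such a shift from biasing the comparison on average. It does not remove the shift from the data. In one order the shift is subtracted from the first-minus-third difference, and in the other it is added. The paired t-test pools the two orders and treats this systematic split as random noise, which lowers power in a small sample. If the two orders end up unequal in size, part of the shift also leaks into the estimate for that particular split.

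The hypothesis 1 ANOVA does not deal with this. Order appears to define two of its three groups, but its outcomes are the DFS and the DBAT measures, not presence.

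**Working it through.** **The plan's own figure.** The only sample-size figure is the total of 36, for three groups, two measurements, effect size .25 and power .80. At alpha .05 it reproduces for the within-person factor with an assumed correlation of .5 (power .829), or for the group-by-time interaction with a correlation of .6 (power .826). It sizes the ANOVA. No power figure for hypothesis 2 is stated, so none is contradicted.

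**Inputs.**
- From the documents: two randomised orders, a switch after week 1, a paired t-test.
- Assumed, because the documents are silent: two-sided alpha .05; n = 24 treated (two of three equal groups of 12 out of 36), with 18 as a check; paired-difference SD 1 within each order; perspective effect τ = 0.6; week-2-minus-week-1 shift π = 0, 0.25, 0.5 or 0.8.

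**Model.** Let d be first-person minus third-person presence. In order A (first-person first) d has mean τ − π; in order B it has mean τ + π.

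- *Paired t.* The mean of d estimates τ + π(nB − nA)/n. The sum of squares (n − 1)s² is noncentral chi-square with n − 1 df and noncentrality 4·nA·nB·π²/n.
- *Period-adjusted.* The estimate is the average of the two order means of d, with expectation τ at any split. Its SE is ½√(1/nA + 1/nB), on n − 2 df.

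**One case by hand: 12/12, π = 0.5.** The noncentrality is 4 × 12 × 12 × 0.25 / 24 = 6. The expected s² is therefore (23 + 6)/23 = 1.26 instead of 1, which is the variance the paired test fails to remove. The adjusted SE is ½√(1/12 + 1/12) = 0.204, so its noncentrality is 0.6/0.204 = 2.94 on 22 df, giving power .802 whatever the shift.

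**Power, n = 24, τ = 0.6.** The right-hand columns average over Binomial(24, ½) splits, excluding those with everyone in one order.

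| Shift π | 12/12 paired | 12/12 adjusted | Simple 1:1 paired | Simple 1:1 adjusted |
|---|---|---|---|---|
| 0 | .804 | .802 | .804 | .784 |
| 0.25 | .785 | .802 | .780 | .784 |
| 0.5 | .728 | .802 | .711 | .784 |
| 0.8 | .609 | .802 | .591 | .784 |

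The adjusted test overtakes the paired test at a shift of about 0.07 SD for 12/12 and 0.23 SD under simple allocation. With 18 treated these are 0.09 and 0.26 SD, and at 9/9 with π = 0.5 the powers are .576 and .667. For other effects at 12/12 and π = 0.5, paired against adjusted power is .374 against .466 (τ = 0.4) and .938 against .963 (τ = 0.8).

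**Type I error of the paired test.** At 12/12 it is .050, .044, .029 and .013 across the four shifts. Averaged over simple allocation it is .050 throughout.

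**Conditional on an unequal split, π = 0.5.** The sign of the bias depends on which order is larger: it is negative when more participants see first-person first.

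| Split A/B | Size of bias, SD | Paired type I | Paired power (A larger; B larger) | Adjusted power |
|---|---|---|---|---|
| 12/10 or 10/12 | 0.045 | .033 | .609; .752 | .760 |
| 14/10 or 10/14 | 0.083 | .042 | .590; .842 | .791 |
| 16/8 or 8/16 | 0.167 | .085 | .444; .920 | .754 |
| 15/7 or 7/15 | 0.182 | .091 | .383; .905 | .703 |

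For example, at 16/8 the bias is 0.5 × (8 − 16)/24 = −0.167. Among these splits, inflation appears only at 16/8 and 15/7. With 24 treated, a split of 16/8 or worse has probability .15 under simple allocation.

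**The case against.** The strongest reply is that nothing here is wrong. Randomised order is the design's own protection against a period effect, the paired test keeps its error rate, and the choice is between two valid analyses. That is correct, and the point should be read in that light.

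Second, the harm depends on a shift that the documents neither assert nor size. At 0.25 SD the loss is about 2 points at 12/12 and under half a point with simple allocation. The larger losses need a shift close to, or above, the assumed perspective effect. This also stands. The changes of mode, setting and viewing time make a shift plausible, not certain.

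Third, the period term can cost power. Under simple allocation the paired test is as good or slightly better up to about 0.23 SD. This stands, but the trade is lopsided. With no shift the cost is .002 (12/12) or .020 (simple allocation). At 0.5 SD the gain is about 7 points, and at 0.8 SD about 19.

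Fourth, the hypothesis is directional and no sidedness is stated. One-sided at 12/12 and 0.5 SD, power is .841 paired and .885 adjusted. The gap narrows from 7 points to 4 but does not close.

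Fifth, the conditional results at unequal splits average out over randomisation. That is true, and they are a secondary argument. They matter only because the ratio and blocking are unstated and only one split will be realised.

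Finally, the documents state that order is assigned, not that it is recorded. Its availability is an inference, though a safe one, since the paired test itself needs to know which perspective each rating refers to.

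**Conclusion.** The point holds as a recommended improvement. The paired t-test for hypothesis 2 is valid but leaves any average week-1 to week-2 shift in the error term, although the design supplies the information to remove it. Under the assumptions above, the gain from a period term is negligible at a shift of 0.25 SD (2 points at best), about 7 points at 0.5 SD and 18 to 19 points at 0.8 SD. The period-adjusted estimate is also unaffected by an average shift at any realised split.

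The size rests on assumed values for the shift, the perspective effect, the number treated and alpha; none is in the documents. The conclusion concerns hypothesis 2 only and breaks no stated power claim.

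**What to change.** In the SAP, replace the paired t-test for hypothesis 2 with the period-adjusted crossover analysis in treatment-group participants. Either form will do:

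- a two-sample t-test of week-1-minus-week-2 PQ differences between the two randomised orders. The order means are τ − π and −τ − π, so half their difference is τ; or
- a mixed model with perspective and period as fixed effects and participant as a random effect.

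Fix this before the data are seen, so that the choice is not post hoc. State the planned order ratio of the prepared envelopes; an equal ratio keeps the cost of the period term lowest. Add that the period term absorbs only the average shift: it does not remove carryover or a rating-mode-by-perspective interaction.

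The cost is one sentence, one degree of freedom and no new data or visits. If there is in fact no shift, power falls from .804 to .802 at 12/12, to .784 averaged over simple allocation, and to .754 at a 16/8 split.
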